Cardiac events Myocardial infarction or unstable angina Heart failure Cerebral vascular accident and transient ischemic attack Cardiovascular procedures (SAE Supplemental Procedure eCRF)	
 
Cardiovascular History and CV Risk Factors eCRF
 
Cardiovascular (Cardiac) AE eCRF
 
Myocardial Infarction and Unstable Angina AE eCRF
 
Heart Failure AE eCRF
 
Cerebral Vascular Accident and Transient Ischemic Attack AE eCRF
 
Arrhythmia AE eCRF
 

Discontinuation or interruption of study drug due to a hepatic-related AE A hepatic-related SAE ALT/AST > 8 × ULN or ALT/AST > 3 × ULN with a total bilirubin > 2 × ULN	Hepatic AE eCRF
TB Subjects with events of latent TB or suspected active TB after initiation of study drug should have a TB Supplemental Form completed.	TB Supplemental eCRF
COVID-19 infection	COVID-19 eCRF
Ocular events	Ophthalmologic eCRF
Herpes Zoster	Herpes Zoster eCRF
Hypersensitivity	Hypersensitivity Reaction Signs and Symptoms eCRF
Death	Death eCRF

If an AE, whether associated with study drug or not, meets any of the following criteria, it is to be reported to AbbVie clinical pharmacovigilance or contract research organization (as appropriate) as a SAE within 24 hours of the site being made aware of the SAE (refer to Section 4.3 of the Operations Manual for reporting details and contact information):

Death of Subject	An event that results in the death of a subject.
Life-Threatening	An event that, in the opinion of the investigator, would have resulted in immediate fatality if medical intervention had not been taken. This does not include an event that would have been fatal if it had occurred in a more severe form.
Hospitalization or Prolongation of Hospitalization	An event that results in an admission to the hospital for any length of time or prolongs the subject's hospital stay. This does not include an emergency room visit or admission to an outpatient facility.

Congenital Anomaly	An anomaly detected at or after birth, or any anomaly that results in fetal loss.

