### Safety Topics of Interest

Adverse events will be monitored throughout the study to identify any safety topics of interest that may indicate a trend or risk.

The potential for abdominal distention, gastrointestinal pain, vomiting, diarrhea and eye pain, redness or blurred vision has been identified.

No ocular findings were seen in the preclinical studies conducted with cedirogant and no ocular AEs considered related to drug have been reported in the cedirogant Phase 1 studies to date. There have been no reports of ocular findings in the literature with other products in development of the same mechanism of action.

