10.2.6 Safety Topics of Interest

Safety topics of interest will be summarized according to the search criteria are provided in [Appendix B](#).

The final list will be based on the most updated final version of cedirogant Product Safety Statistical Analysis Plan.

Treatment-emergent Safety Topics of Interest will be summarized by SOC and PT and listing format. Additionally, STI rates per 100 patient years of exposure will be provided for each STI category ([Appendix B](#)) in the AE overview summary.

Listings of safety topics of interest will also be provided.

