Appendix B. Definition of Safety Topics of Interest for cedirogant

Safety topics of interest (STI) will be identified using the following search criteria:

Safety Topic of Interest	Basis for Inclusion	Criteria for Identification of Event	Are events adjudicated (yes/no)? If yes, external or internal adjudication?	Special Collection Forms or Safety Studies	Relevant Restrictions [#]
Identified Risks - None					
Important Potential Risks					
Serious infection*	Based on the mechanism of action and data from the biomedical literature, as well as information from nonclinical pharmacology and toxicity studies, ABBV-157 administration is expected to produce effects on white blood cells and cytokines. These immunomodulatory properties may result in an increased risk of infection.	Serious events only from the Infections and Infestations SOC	No	No	Exclusion of subjects with HIV, hepatitis B or hepatitis C viral infection. Exclusion of subjects with active severe acute respiratory syndrome coronavirus 2 (SARS-CoV-2) infection.
Other Safety Topics of Interest					
GI tract altered mobility	In rats, GI effects were present at \geq 100 mg/kg/day in the 4-week GLP study and led to marked body weight loss and dehydration, necessitating euthanasia in two animals due to moribund condition. There was also histopathologic evidence of intestinal tract dilation in rats. In the GLP dog study, ABBV-157 produced emesis and loose to watery stools that were well tolerated throughout the study at doses of 40, 120, and 300 mg/kg/day.	Gastrointestinal nonspecific symptoms and therapeutic procedures SMQ_Narrow	No	No	None
Herpes zoster	Manipulating the inflammation cascade with any immune-modulating biologic may increase the risk of infections. Cases of Herpes Zoster is not included in OI CMQ	Herpes Zoster CMQ	No	Yes	None

Safety Topic of Interest	Basis for Inclusion	Criteria for Identification of Event	Are events adjudicated (yes/no)? If yes, external or internal adjudication?	Special Collection Forms or Safety Studies	Relevant Restrictions [#]

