MACE	There is an increased risk of cardiovascular disease in the psoriasis patient population.	Other Ischaemic heart disease SMQ_narrow Central nervous system hemorrhages and cerebrovascular conditions SMQ_narrow Myocardial infarction SMQ_narrow Death and Sudden Death - HLT	No	Yes	None

Safety Topic of Interest	Basis for Inclusion	Criteria for Identification of Event	Are events adjudicated (yes/no)? If yes, external or internal adjudication?	Special Collection Forms or Safety Studies	Relevant Restrictions [#]
Ocular events	In a healthy volunteer study of an ROR γ t compound related to ABBV-157, 3 of 9 subjects developed eye related events after multiple doses, including one subject who was seen by eye specialists and required prolonged treatment with steroid eye drops and an oral NSAID (aspirin-like drug).	Conjunctival disorders SMQ_narrow Corneal disorders SMQ Scleral disorders SMQ_narrow	No	Yes	Current phase 2b protocol requires any subject with CTCAE Grade 2 or higher AE ocular event must follow up with an ophthalmologist within 7 days. Grade 2 or higher ocular AEs considered related to study drug administration qualify for withdrawal criteria.
Possible malignancies	Comorbidity with patient population, NMSC most common. Theoretical possibility of decreased immune surveillance against malignancies with alteration of immune pathways.	- Malignant tumours SMQ - narrow	No	No	Exclusion of subjects with a history of any malignancy within the last 5 years or documented active malignancy except for successfully treated non-melanoma skin cancer (NMSC) or localized carcinoma in situ of the cervix.
Non-melanoma skin cancer (NMSC)	Comorbidity with patient population, NMSC most common. Theoretical possibility of decreased immune surveillance against malignancies with alteration of immune pathways.	Skin malignant tumours SMQ Broad excluding preferred terms identified by the Melanoma CMQ	No	No	Exclusion of subjects with a history of untreated non-melanoma skin cancer (NMSC).

Safety Topic of Interest	Basis for Inclusion	Criteria for Identification of Event	Are events adjudicated (yes/no)? If yes, external or internal adjudication?	Special Collection Forms or Safety Studies	Relevant Restrictions [#]

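### The SAP's ocular search is not shown to capture every ocular event the protocol treats as a safety topic of interest, so the ocular count, listing and rate may be incomplete

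*SAP*

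**What the plan says.** **Protocol.** Section 6.1 has a table of safety topics of interest for which a supplemental report must be completed. Ocular events are one row, the report is the "Ophthalmologic eCRF", and no eye structure is named. Under the heading Safety Topics of Interest, the same section says that the potential for "eye pain, redness or blurred vision has been identified". The ophthalmologist follow-up in Section 6.2 also applies to ocular events in general.

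**SAP.** Appendix B opens with the rule that "Safety topics of interest (STI) will be identified using the following search criteria". For ocular events the criteria are "Conjunctival disorders SMQ_narrow Corneal disorders SMQ Scleral disorders SMQ_narrow". The row answers yes to special collection forms, but the search does not use the form. The stated basis for including the topic is a related compound, on which "3 of 9 subjects developed eye related events after multiple doses"; no eye structure is given there either.

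SAP 10.2.6 builds the topic tables and listings on these searches and adds that "STI rates per 100 patient years of exposure will be provided for each STI category". It also says that "The final list will be based on the most updated final version of cedirogant Product Safety Statistical Analysis Plan". That plan is not among the documents.

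**The concern.** The two documents give one topic two definitions. In the protocol, an ocular event is anything ocular, and the anticipated presentation is described by symptoms. In the SAP, it is whatever three queries named after parts of the eye return. An event could be handled as an ocular topic of interest at the site, with its form completed, and still not be counted as one in the analysis. The SAP does not say how the two are reconciled.

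Four outputs depend on the search: the ocular topic table, its listing, its rate per 100 patient-years, and the line in the adverse event overview (SAP 10.2.2) for any treatment-emergent safety topic of interest. The trial stopped before its planned enrolment, so counts may well be small, and one uncounted case would then change an ocular summary visibly.

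**Working it through.** The plan states no ocular rate and lists no query terms, so there is no figure to reproduce. The check is a comparison of the two definitions, followed by an illustration of scale.

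**1. Definitions compared**

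| Feature | Protocol 6.1 and 6.2 | SAP Appendix B, ocular row |
|---|---|---|
| Part of the eye | Not limited | Conjunctiva, cornea, sclera (by query name) |
| Symptoms named | Eye pain, redness, blurred vision | None |
| Scope | Any ocular event | Conjunctival narrow; scleral narrow; corneal not stated |
| Ophthalmologic form | Required | Noted as collected, not used in the search |

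A query named after a structure may contain symptom terms, so the names do not show that a symptom is missed. Nor does anything in the SAP show that all three symptoms, or events in other parts of the eye, are retrieved.

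**2. Illustration of scale (assumptions, not findings)**

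Inputs:
- 50 subjects per arm, the planned size (SAP 2.4).
- 16 weeks of dosing plus 30 days for every subject. This follows the patient-year definition in SAP 10.2.4 with no early discontinuation and before its rounding.
- Five ocular events in the arm, assumed.
- s, the share of ocular events that the three queries do not retrieve. The documents do not give it, so it is varied from 0 to 75%.

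Exposure = 50 × (16 × 7 + 30) / 365.25 = 50 × 142 / 365.25 = 19.44 patient-years.

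Rate with nothing missed = 100 × 5 / 19.44 = 25.7 per 100 patient-years.

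Reported rate = 25.7 × (1 − s).

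The chance that at least one captured case is seen among 50 subjects, for an assumed true subject-level risk of 5%, is 1 − (1 − 0.05 × (1 − s))^50. Here s is applied to subjects with an event.

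| s | Reported rate per 100 patient-years | Chance of at least one captured case |
|---|---|---|
| 0 | 25.7 | 92% |
| 25% | 19.3 | 85% |
| 50% | 12.9 | 72% |
| 75% | 6.4 | 47% |

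The first row, with no loss, is as compatible with the documents as the others. Actual exposure will be lower than assumed because the study ended early. That changes the absolute rates but not the factor (1 − s).

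**3. The related compound**

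3/9 = 33%, exact 95% interval 7.5% to 70.1%. This explains why the topic is on the list. It concerns another compound and carries no information about s.

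**The case against.** The strongest reply is that no missed event has been shown. A reader might infer from the query names that eye pain, redness and blurred vision are left out and that the ocular rate will be understated. The documents do not support this. They do not give the query contents, and the corneal query lacks the narrow label carried by the other two, so it may be broader than its name suggests. This stands, and it limits the point to capture that is not assured.

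A reader might also infer that ocular cases could vanish from the report. They would not. SAP 10.2.3 tabulates all treatment-emergent events by system organ class and preferred term, by severity and by relationship; 10.2.5 summarises and lists events leading to discontinuation of study drug. This also stands. Those tables do not, however, repair the ocular topic count, listing or rate, because they spread related complaints over separate terms.

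Third, Appendix B yields to the product-level safety plan, which may already be broader. That cannot be checked here. It means the correction has to be made there as well.

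Fourth, other rows also rely on named queries without listing terms, and Protocol 6.1 reports no preclinical ocular findings and no drug-related ocular events in Phase 1 with cedirogant. Both are true and argue for low severity. The ocular row still differs from most: the protocol names specific symptoms and a dedicated form for this topic, and the search refers to neither.

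Finally, including events by form makes the row depend partly on sites completing the form. That is a fair reservation, and the reason to add the form to the queries and not to replace them.

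**Conclusion.** The point holds in a limited form. The protocol's ocular topic covers any ocular event and names three symptoms. The SAP identifies the topic through three structure-named queries, one without a stated scope, and does not show that the two definitions agree. The ocular topic-of-interest count, listing and rate per 100 patient-years may therefore be incomplete.

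The size of any loss cannot be derived from the documents and may be zero. If a share s is missed, the reported rate is (1 − s) times the full rate; every value of s used above is an assumption. Only the topic-of-interest outputs are affected. Severity is low: the trial was stopped early, no statistical testing is planned, and every ocular treatment-emergent event remains visible in the general tables.

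**What to change.** In the ocular row of SAP Appendix B, and in the product-level safety plan whose list supersedes it:

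1. Keep the three queries.
2. State whether the corneal query is narrow or broad.
3. Add preferred terms for eye pain, ocular redness and blurred vision where the queries do not already retrieve them.
4. Count any treatment-emergent event for which an ophthalmologic form was completed.

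This aligns the analysis with the protocol's topic whatever the queries contain. If everything is already captured, no result changes. Broad criteria have a precedent in the same appendix, where the serious infection row searches a whole system organ class.

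The cost is one row of text in each plan and a small change to the search program. The downside is that a few non-specific eye complaints will be counted as ocular topic events.

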Appendix C. Potentially Clinically Important Criteria for Safety Endpoints

The criteria for Potentially Clinically Important (PCI) laboratory findings are described in Table C-1 and Table C-2, and the PCI criteria for vital sign findings are described in Table C-3.

Table C-1. Criteria for Potentially Clinically Important Hematology Values

Hematology Variables	Units	Definition of Potentially Clinically Important NCI CTCAE (Version 4.03) Grade 3 or greater
		Very Low
Hemoglobin	g/dL	< 8.0
Platelets count	10 ⁹ /L	< 50.0
WBC count	10 ⁹ /L	< 2.0
Neutrophils	10 ⁹ /L	< 1.0
Lymphocytes	10 ⁹ /L	< 0.5

Note: A post-baseline value must be more extreme than the baseline value to be considered a potentially clinically important finding.

Table C-2. Criteria for Potentially Clinically Important Chemistry Values

Chemistry Variables	Units	Definition of Potentially Clinically Important NCI CTCAE (Version 4.03) Grade 3 or greater	
		Very Low	Very High
TBL	mcmol/L		$> 3.0 \times \text{ULN}$
ALP	U/L		$> 5.0 \times \text{ULN}$
SGOT/AST	U/L		$> 5.0 \times \text{ULN}$
SGPT/ALT	U/L		$> 5.0 \times \text{ULN}$
Albumin	g/L	< 20	
Glucose	mmol/L	< 2.2	> 13.9
Triglycerides	mmol/L		> 5.7
Creatinine	mcmol/L		$> 3.0 \times \text{ULN}$ $(> 3.0 \times \text{BL})$
Sodium	mmol/L	< 130	> 155
Potassium	mmol/L	< 3.0	> 6.0
Calcium	mmol/L	< 1.75	> 3.1
CPK	U/L		$> 5.0 \times \text{ULN}$
Total Cholesterol	mmol/L		> 10.34
GGT			$> 5.0 \times \text{ULN}$

Note: A post-baseline value must be more extreme than the baseline value to be considered a potentially clinically important finding.

Table C-3. Criteria for Potentially Clinically Important Vital Sign Values

Vital Signs Variables	Criterion	Definition of Potentially Clinically Important
Systolic Blood Pressure (mmHg)	Low	Value ≤ 90 mmHg and decrease ≥ 20 mmHg from Baseline
	High	Value ≥ 160 mmHg and increase ≥ 20 mmHg from Baseline
Diastolic Blood Pressure (mmHg)	Low	Value ≤ 50 mmHg and decrease ≥ 10 mmHg from Baseline
	High	Value ≥ 100 mmHg and increase ≥ 10 mmHg from Baseline
